3.3.2.2 Phase II clinical trials

A randomized, double-blind, comparative, multi-center study (#TG-873870-02) of the safety and efficacy of oral nemonoxacin versus oral levofloxacin in adult patients with CAP was carried out in 19 study centers in South Africa and Taiwan. A total of 265 subjects were enrolled and randomized in the study: 86 patients in the nemonoxacin 750 mg group, 89 in the nemonoxacin 500 mg group and 90 in the levofloxacin 500 mg group. Patients received therapy once daily for 7 days. The study revealed that 750 and 500 mg nemonoxacin had similar clinical efficacy when compared with 500 mg levofloxacin once daily for 7 days. The safety profile of nemonoxacin was also similar to that of levofloxacin and it was consistent with the favorable safety results of nemonoxacin in previous phase I studies [28].

Efficacy and safety of Nemonoxacin malate sodium chloride injection versus Moxifloxacin hydrochloride sodium chloride injection in the treatment of moderate to severe adult CAP were evaluated during a multi-center, randomized, double-blind, parallel, controlled, phase II study. Patients received either 500 mg nemonoxacin, 650 mg nemonoxacin, or comparator drug moxifloxacin 400 mg once a day for 7 to 14 days. A total of 207 subjects were randomly enrolled in 30 research centers: 69 subjects were in the nemonoxacin 500mg group, 68 subjects were in the nemonoxacin 650 mg group and 70 subjects were in the control group (moxifloxacin 400mg). Nemonoxacin had shown similar clinical efficacy, microbiological efficacy, and overall efficacy when compared with moxifloxacin hydrochloride sodium chloride injection once a day for 7 to 14 days. The AEs reported during the study were mostly mild, transient, and tolerated by most patients. The main drug-related AEs in patients who received nemonoxacin were local reactions at the infusion site. The main drug-related laboratory abnormalities were elevated liver transaminases without bilirubin elevation [24].

3.3.2.3 Phase III clinical trials

During a multicenter, randomized, double-blind, double-dummy, parallel, comparative, phase III study the efficacy and safety of oral administration with Nemonoxacin versus Levofloxacin in treating adult patients with CAP were evaluated (TG-873870-C-4). The study was conducted in 53 study centers in China and Taiwan. A total of 532 patients were randomized into the study at a ratio of 2:1 into two groups: the investigational group (nemonoxacin 500 mg) and the control group (levofloxacin 500 mg), respectively. There were 357 patients in the investigational group (nemonoxacin) and 175 patients in the control group (levofloxacin). Duration of therapy was 7 – 10 days. The results of the study indicate that oral administration of 500 mg nemonoxacin malate capsules for 7 to 10 consecutive days achieved excellent clinical and microbiological efficacies in treating adult CAP patients. Nemonoxacin had similar clinical and microbiological efficacies as compared with levofloxacin. Statistical analysis demonstrated that nemonoxacin was non-inferior to in clinical and microbiological efficacies. The AEs reported in the study were mostly mild in intensity, well-tolerated, and did not affect the course of the treatment. No deaths were reported during this study [25].

CONFIDENTIAL Page 29 of 88

3.4 Assessment of Potential risks and benefits for participants

Comparator Tavanic[®] (Levofloxacin) is effective antibiotic approved for treatment of a wide variety of infectious diseases, including CAP. The drug may be administered for empiric antimicrobial therapy in patients with CAP.

Investigational product Nemonoxacin, capsules, has already been approved in Taiwan and China for treatment of CAP and the phase III clinical study of efficacy and safety of Nemonoxacin intravenous formulation is ongoing. At this time more than 1000 subjects were participated in various clinical studies of nemonoxacin, capsules or solution for infusion.

Nemonoxacin has shown similar clinical and microbiological efficacies as compared with levofloxacin during clinical studies in patients with CAP (see Sections 3.3.2.2 and 3.3.2.3). Nemonoxacin was well tolerated and had acceptable safety profile either when administered by intravenous and oral routs. The majority of AEs reported during the studies were mild and transient.

The risk to patients in this clinical study will be minimized by compliance with selection criteria. Taking into account available safety data for investigational medicinal products, both Levofloxacin and Nemonoxacin (e.g., possibility of QT prolongation, hypoglycemia, tendinitis and tendon rupture, etc.), these medicinal products will be avoided in patients with renal impairment, diabetes mellitus, QT prolongation, uncorrected hypokalemia, receiving class Ia or III antiarrhythmic agents, receiving corticosteroids, etc.

Levofloxacin was shown to have photosensitization activity. Therefore, in order to prevent photosensitization in patients the Patient Information Leaflet provides precautions for study participants not to expose themselves unnecessarily to strong sunlight or to artificial ultra-violet rays. Although Nemonoxacin did not elicit cutaneous phototoxicity in preclinical studies and by now there is no clinical data suggested phototoxicity of the drug the aforementioned precautions will be taken by all participants (i.e., regardless of treatment group) because of double-blind design of the study and because of absence of certainty the drug has not such activity.

In consideration of the foregoing assumptions the risk-benefit ratio for the participants is acceptable.

This clinical study will be conducted in compliance with the Protocol, ICH GCP and all other applicable local regulatory requirements.

3.5 Dose, route, regimen and treatment period rationale

Nemonoxacin, solution for infusion, and Nemonoxacin, capsules, will be administered at daily dose of 500 mg. The choice of the dose is based on the results of previous clinical trials (please, refer to Section 3.3.2).

Tavanic[®] (levofloxacin), solution for infusion, is available in one dosage strength of 500 mg (100 ml). Tavanic[®] (levofloxacin), film coated tablets, is available in two dosage strengths of 250 and 500 mg. The usual dose of Levofloxacin (either solution for infusion and tablets) for treatment of community-acquired pneumonia is 500 mg administered once or twice a day for 7-14 days, as indicated in product label [26][27]. In this clinical study the daily dose of Tavanic[®] (levofloxacin) was chosen to be 500 mg because this daily dose was approved for the treatment of CAP in the countries where this clinical study will be carried out.

Therapy of the patients will start with intravenous infusions and after 3-7 days patients will be switched to oral treatment. In accordance with Russian recommendations for management of

CONFIDENTIAL Page 30 of 88

CAP taking into consideration that hospitalized patients usually tend to have more severe course of CAP it is reasonable to start treatment with parenteral antibiotics and to switch to oral treatment after the normalization of temperature and abatement of the symptoms [1]. Switch from intravenous to oral antibiotics is generally considered appropriate and safe in clinical practice when criteria indicative of clinical stability of disease are met. In the CAPRIE study the majority of patients were switched to oral therapy on day 3-4 after the start of treatment with levofloxacin [3]. In another study the median time to actual switch to oral therapy was 5 days (range from 2 to 7 days) for levofloxacin-treated patients and the total duration of study therapy was 7 to 14 days at the investigator's discretion [16]. In general, as many as two-thirds of all patients with CAP have clinical improvement and meet criteria for a therapy switch in the first 3 days, and most non-intensive care unit patients meet these criteria by day 7 [11]. Therefore, the switch to oral treatment was chosen to be Day 4-8 of the study, after 3-7 days of intravenous therapy.

4 STUDY OBJECTIVES

4.1 Primary Objective

To evaluate the clinical efficacy of treatment with Nemonoxacin compared with Tavanic[®] in patients with CAP.

4.2 Secondary Objectives

- To evaluate the clinical efficacy of treatment with intravenous Nemonoxacin compared with intravenous Tavanic[®] in patients with CAP
- To assess the safety of treatment with Nemonoxacin compared with Tavanic[®] in patients with CAP
- To assess the pharmacokinetic parameters of intravenous Nemonoxacin in adult patients with CAP
- To evaluate the microbiological efficacy of treatment with Nemonoxacin compared with Tavanic[®] in patients with CAP.

5 CLINICAL STUDY ENDPOINTS

5.1 Efficacy endpoints

5.1.1 Primary efficacy endpoint

The primary efficacy endpoint is the proportion of patients with clinical success as judged by the investigator at the test of cure visit (Visit 4).

CONFIDENTIAL Page 31 of 88

5.1.2 Secondary efficacy endpoints

The secondary efficacy endpoints are the following:

- Proportion of patients with clinical success as judged by the investigator at the Visit 2 (switch to oral therapy) and Visit 3
- Proportion of patients with infection relapse at Visit 5
- Time to switch therapy from i.v. to oral therapy
- Need for other antibiotic treatment
- Proportion of patients with microbiological responses at the Visit 2 (switch to oral therapy), Visit 3 and Visit 4.

5.2 Safety endpoints

The following safety endpoints will be evaluated:

- Adverse events
- Changes in vital signs
- Clinical laboratory results
- ECG results
- Physical examination results.

5.3 Pharmacokinetic parameters

The following pharmacokinetic parameters will be evaluated:

- C_{max}
- C_{22.5h}
- AUC_{0-22.5}
- AUC_{0-inf}
- CL
- \bullet V_{ss}
- T_{1/2}

6 STUDY DESIGN

6.1 Design Summary

This is an international, multicenter, randomized, parallel group, double-blind, double-dummy, controlled study of efficacy and safety.

Treatment-naive patients with community-acquired pneumonia (non-nosocomial pneumonia) and patients with treatment failure will be screened and if eligible will be randomized in a ratio of 1:1 to receive either treatment with investigational product (Nemonoxacin) or comparator (Tavanic®). After randomization patients will start to receive intravenous therapy with investigational product or comparator and then upon a decision of investigator patients will be switched to oral therapy with the same product. To maintain double-blinding during the intravenous treatment the patients will receive placebo solution (100 ml or 250 ml) along with intravenous

CONFIDENTIAL Page 32 of 88

antibiotic (Nemonoxacin or Tavanic[®]) solution. To maintain double-blinding during oral antibiotic therapy each Tavanic[®] tablet was placed into a capsule shell (over-encapsulated), that is identical in appearance to a Nemonoxacin-containing capsules; therefore, the patients will receive daily treatment with 2 capsules either containing nemonoxacin or levofloxacin (tablet of Tavanic[®]) (see Table 6-1).

Table 6-1	1 Summary	of treatment	groups
-----------	-----------	--------------	--------

Group	Number of	Intravenous therapy (once a day)		Oral therapy (once a day)
	patients	First infusion	Second infusion	
Investigational drug (Nemonoxacin)	171	Nemonoxacin 500 mg (250 ml), solution for infusion, will be given over 90-110 minutes	Placebo (100 ml), solution for infusion, will be given over a minimum of 60 minutes	Nemonoxacin 250 mg x 2 capsules
Comparator (Tavanic [®])	171	Placebo (250 ml), solution for infusion, will be given over 90-110 minutes	Tavanic [®] 500 mg (100 ml), solution for infusion, will be given over a minimum of 60 minutes	Tavanic® 250 mg x 2 over- encapsulated film coated tablets
Total number of patients	342			

Intravenous therapy will be administered once a day and will include two consequence infusions (antibiotic solution and placebo solution). Solution with volume of 250 ml will always be infused over 90-110 minutes and before the infusion of solution with volume of 100 ml that will be infused over at least 60 minutes. Intravenous therapy should be given for at least 3 days and may be prolonged by a decision of investigator up to 7 days. Then investigator will switch a patient from intravenous to oral therapy on Day 4(8) of the study if the specific criteria of clinical stability are achieved (please, refer to Appendix 2). However if the treatment with intravenous IMP should be prolonged after the 7 days of treatment are completed (according to the investigator's opinion) the investigator should contact the study Medical Adviser (please, refer to Contact information) for the approval of intravenous treatment prolongation.

In general since Day 4(8) of the study treatment will be continued with the same antibiotic administered orally. Patients will daily receive treatment either with 2 capsules of investigational drug (Nemonoxacin, 250 mg) or 2 over-encapsulated film coated tablets of Comparator (Tavanic[®] 250 mg).

The average duration of treatment (including intravenous and oral therapy) for each patient will be 7(14) days and during this period patients should stay at hospital.

[figure not shown]
After completion of the treatment patients can be discharged from the hospital and should return for examinations at End of treatment visit (Visit 3) within 1-2 days after the last dose. Then the patients should attend the investigational site within 7-9 days after the last dose (test of cure visit). Then the investigator will contact the patients by phone within 21-23 days after the last dose (long-term follow-up visit).

The study includes 5 visits. The detailed description of visits is presented in Section 9.2. A schematic diagram of the study design is presented in Figure 6-1.

CONFIDENTIAL Page 33 of 88

R-Pharm JSC CJ01060044 Nemonoxacin

Figure 6-1: Study design

CONFIDENTIAL Page 34 of 88

7 SELECTION OF STUDY POPULATION

7.1 Inclusion Criteria

Patients will be eligible for inclusion in the study only if all of the following inclusion criteria are applied:

- 1. Written informed consent obtained from the patient.
- 2. Female and male patients aged between 18 and 70 years inclusive.
- 3. Patients with moderate to severe community-acquired pneumonia who need inpatient treatment (correspondence to at least one of the criteria for hospitalization / preferred hospitalization described in the Appendix 1 of this protocol) but do not need ICU treatment (in case of correspondence to at least one «major» or three «minor» criteria for hospitalization in intensive care unit described in Appendix 1 of this protocol, patient should not be enrolled in the study).
- 4. The presence of at least 3 of the following symptoms/signs:
 - Cough
 - Purulent sputum production
 - Tachypnea (respiratory rate > 24 breaths/minute)
 - Chills
 - Fever (rectal/ tympanic temperature $\geq 38.5^{\circ}\text{C}$ or axillary/ oral/ cutaneous temperature $\geq 38.0^{\circ}\text{C}$)
 - WBC count of $\ge 10.0 \text{ x } 10^9/\text{L}$ or $\ge 15\%$ immature neutrophils (bands; regardless of peripheral WBC count).
- 5. Radiological evidence of (a) new infiltrate(s) consistent with bacterial pneumonia at baseline.
- 6. Treatment-naive patients or patients who have received single dose of a short-acting antibacterial drug within 24 hours of enrollment or patients with treatment failure who have received antibiotics (with the exception of quinolones or fluoroquinolones) for less than 72 hours.
- 7. Consent to use contraception during participation in the study (for women childbearing potential and men).

7.2 Exclusion Criteria

Patients won't be eligible for inclusion in the study if any of the following exclusion criteria is applied:

- 1. Known hypersensitivity to quinolones, fluoroquinolones or any of the excipients.
- 2. Female patients who are pregnant or nursing.
- 3. History of tendon disease/disorder related to quinolone treatment.
- 4. Known congenital or documented-acquired QT/QTc(F) prolongation on ECG (QTc(F) interval more than 450 ms); concomitant use of drugs, reported to increase the QT interval; uncorrected hypokalaemia and uncorrected hypomagnesemia; clinically relevant bradycardia; clinically relevant heart failure

CONFIDENTIAL Page 35 of 88

- with reduced left-ventricular ejection fraction; previous history of symptomatic arrhythmias.
- 5. History of bronchiectasis, cystic fibrosis, bronchial obstructions excluding chronic obstructive pulmonary disease.
- 6. History of epilepsy and/or history of psychotic disorder.
- 7. Patients with history of myasthenia gravis
- 8. Patients with diabetes mellitus
- 9. Known glucose-6-phosphate dehydrogenase deficiency.
- 10. Active hepatitis or decompensated cirrhosis.
- 11. Alanine transaminase or aspartate transaminase increase > 3 fold ULN.
- 12. Patients with creatinine ≥ 1.1 fold ULN.
- 13. Patients requiring concomitant systemic or inhaled antibiotics (e.g., tobramycin).
- 14. Known or suspected active tuberculosis or endemic fungal infection.
- 15. Concomitant immunosuppressive therapy including a long-term (more than 2 weeks) treatment with oral or intravenous glucocorticoids at doses of 20 mg and higher of prednisone daily or an equivalent dose of other glucocorticoids.
- 16. Patients known to have HIV-positive status or AIDS or known to have other disease that seriously affects the immune system such as active haematological or solid organ malignancy, or splenectomy.
- 17. History of drug or alcohol abuse.
- 18. Patients have received quinolones or fluoroquinolones within 14 days before enrollment.
- 19. Previous enrolment in this study or participation in another study within the previous 4 weeks.
- 20. Patients with any severe medical condition as determined by medical history that, in the opinion of the investigator, does not allow the patient to carry out all planned procedure of the protocol.

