consistent with the known pharmacology of quinolones. The hERG and Purkinje findings suggest the possibility of QTc prolongation in man. Mild effects were also seen at the high dose (1000 mg/kg) in some CNS (decreased SMA) and GI (decreased gastric motility) studies.

Nemonoxacin did not elicit cutaneous phototoxicity when administered orally either once or repeatedly; did not produce systemic hypersensitive reactions during active systemic anaphylaxis test. In the bone/cartilage studies in juvenile dogs administered nemonoxacin at 10, 20, or 40 mg/kg/day for 4 weeks, the microscopic changes were noted in 2/3 males and 3/3 females of the 40 mg/kg/day dose group, the changes were graded minimal to moderate in severity and characterized by degeneration/necrosis with or without horizontal clefting and/or erosion of the articular cartilage. The nature and distribution (targeting the weight bearing area and middle zone of the proximal and distal femur) of these microscopic changes were compatible with quinolone-induced arthropathy/chondrotoxicity. No apparent changes were seen after 13 weeks recovery, suggesting a complete reversibility of the changes [28].

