8.7.2 Prohibited and limited in use therapy

During treatment period (from Visit 1 to Visit 3) the following medications should be prohibited:

- 1. Antacids, multivitamins containing calcium, magnesium, iron, zinc, or aluminum, and sucralfate should be prohibited within 3 hours before and after oral administration of the investigational drug. Intravenous therapy should not be coadministered with any solution containing multivalent cations, e.g., magnesium, through the same intravenous line.
- 2. Probenecid.

During study period (from Visit 1 to Visit 5) the following medications should be prohibited:

- 1. Drugs that may prolong the QT interval with known risk or possible risk of Torsades de Pointes (TdP). The list of these drugs is presented in Appendix 3.
- 2. Chemotherapeutic agents or antitumor drugs.
- 3. Other systemic antibacterial drugs (except for treatment failure).
- 4. Systemic immunosuppressive drugs, including inhaled steroids.
- 5. Drugs that may act to alter the signs and symptoms of infections (e.g., antipyretics, analgesics, antihistamines, or cough suppressants) since day 3 (including) of the treatment.
- 6. Investigational products other than studied in this trial and other than the patient has been randomized.

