9.2 Description of visits

9.2.1 Visit 1 (screening /randomization and intravenous therapy, Days 1-3(7) of the study)

The Visit 1 is scheduled on Days 1-3(7) of the study and will be performed at hospital. On Day 1 (no more than 24 hours) all screening procedures should be performed and eligible patients should be randomized and after randomization will receive the first intravenous dose of IMP. On Days 2-3(7) patients will receive intravenous therapy.

Therefore during the Visit 1 the following procedures will be performed:

Screening procedures (Day 1)

To evaluate the selection criteria of the study, the Investigator may use laboratory test results obtained at the laboratory of the investigational site within 24 hours of study enrollment (Signing of the Informed Consent Form) if he / she considers that available data are sufficient to permit a decision on whether the subject meets the selection criteria. In this case, another blood sampling procedure has to be conducted in the period from the signing of the Informed Consent Form to the start of treatment in order to evaluate all other laboratory parameters that have to be determined on Day 1 in accordance with the study protocol

- Obtainment of written informed consent (before all other procedures)
- Demographic and other baseline characteristic data collection
- Medical history taking
- Pregnancy test (for women of childbearing potential only)
- Physical examination
- Assessment of vital signs
- ECG (before or 30 minutes after blood samples collection)
- Haematology test
- Biochemical assay
- Urinalysis
- Documentation of SAEs occurred after the obtainment of the informed consent (after the signing of ICF)
- Chest x-ray (two-dimensional roentgenogram) or computed tomography. The results of chest x-ray (computed tomography) performed within 72 hours before enrollment are acceptable
- Pulse oximetry
- Collection of sputum sample for culture (if the patient has sputum)
- Collection of blood sample for culture
- Assessment of prior medication taken within 30 days before the Visit and therapies (beginning from the onset of community-acquired pneumonia)
- Check of inclusion/exclusion criteria

CONFIDENTIAL Page 48 of 88

Randomization and initiation of therapy (Day 1)

- Before starting the therapy patients eligible for inclusion will be randomized
- Start of intravenous therapy with IMP
- Assessment of vital signs 2 hours ± 30 minutes after the second infusion (Tavanic®/Placebo) is finished

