10.3.5 Biochemical assay

Blood samples for biochemical assay will be withdrawn before treatment initiation on Day 1 of the study (Visit 1, screening procedures), before dosing on Day 4(8) of the study (Visit 2, switch to oral therapy), within 1-2 days (Visit 3) and within 7-9

CONFIDENTIAL Page 56 of 88

days (Visit 4) after the last dose. At Visits 1, 2, and 3, samples will be collected prior to dosing.

To evaluate the selection criteria of the study, the Investigator may use blood chemistry test results obtained at the laboratory of the investigational site within 24 hours of study enrollment (Signing of the Informed Consent Form) if he / she considers that available data are sufficient to permit a decision on whether the subject meets the selection criteria. In this case, another blood sampling procedure has to be conducted in the period from the signing of the Informed Consent Form to the start of treatment in order to evaluate all other blood chemistry test parameters that have to be determined on Day 1 in accordance with the study protocol.

Biochemical assay will be performed in the local laboratory of investigational site using standard validated methods. The following investigations will be made:

- glucose
- total bilirubin
- alanine aminotransferase (ALT)
- aspartate aminotransferase (AST)
- gamma-glutamyl transpeptidase (GGTP)
- alkaline phosphatase (ALP)
- potassium (K⁺)
- sodium (Na⁺)
- creatinine
- urea.

All clinically significant abnormal changes in biochemical parameters from the baseline results must be reported as AEs in the eCRF.

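### Uncorrected hypomagnesaemia is an exclusion, but no protocol procedure measures magnesium, so this part of criterion 4 cannot be systematically applied or verified

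*Combined protocol and SAP*

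**What the plan says.** Criterion 4 in section 7.2 groups the cardiac exclusions. After the items on QT prolongation and QT-active co-medication it lists "uncorrected hypokalaemia and uncorrected hypomagnesemia". The synopsis carries the same text. No numerical limit is given for either electrolyte.

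Section 10.3.5 states: "Biochemical assay will be performed in the local laboratory of investigational site using standard validated methods". Its list is glucose, total bilirubin, ALT, AST, GGTP, ALP, potassium, sodium, creatinine and urea. The same list serves Visits 1 to 4.

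Section 9.2.1 adds that, for eligibility, "the Investigator may use laboratory test results obtained at the laboratory of the investigational site within 24 hours of study enrollment". A further sample is then taken before treatment "in order to evaluate all other laboratory parameters that have to be determined on Day 1 in accordance with the study protocol".

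On risk, section 3.4 says: "The risk to patients in this clinical study will be minimized by compliance with selection criteria". It names QT prolongation as a possible effect of both study drugs. For nemonoxacin the preclinical summary in section 3.3.1.4 reports: "The hERG and Purkinje findings suggest the possibility of QTc prolongation in man". Appendix 3 lists levofloxacin among drugs with known risk of torsades de pointes.

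**The concern.** An eligibility rule that depends on a laboratory value needs a source for that value. Criterion 4 pairs two electrolytes because both bear on QT risk, but the protocol orders a test for only one. At stake is whether the exclusion works as the sponsor intended for patients whose low magnesium nobody has yet noticed, and whether a monitor could later tell that it had been breached. Section 15 provides for 100% source data verification, but for this item the protocol generates no source value to verify. This is a question of safety and of eligibility checking, not of the primary comparison.

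**Working it through.** No figure in the plan needs reproducing. The check sets the criterion against every place where a magnesium test could be required.

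1. **Is the criterion limited to known cases?** Elsewhere in section 7.2 the protocol says so when it means this: criteria 1, 9, 14 and 16 use the word known, and criteria 3, 5, 6, 7 and 17 refer to history. In criterion 4 the word known qualifies congenital QT prolongation. The electrolyte item follows after a semicolon without it. On its wording it covers any uncorrected case.

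2. **Do the laboratory panels contain magnesium?**

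| Place | Magnesium |
|---|---|
| 10.3.4 Haematology | No |
| 10.3.5 Biochemistry (10 analytes) | No; potassium and sodium only among electrolytes |
| 10.3.6 Urinalysis | No |
| Table 9-1 and footnotes | No; names the panels only |
| 9.2.1 to 9.2.5 visit descriptions | No |

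3. **Does the rule on existing results bring it in?** No. The extra pre-treatment sample is for parameters the protocol itself requires on Day 1, and magnesium is not one of them.

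4. **Other mentions of magnesium.** Section 8.7.2 refers to "multivitamins containing calcium, magnesium, iron, zinc, or aluminum" and to infusion solutions containing such cations. These are interaction rules, not tests.

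5. **Comparison with other laboratory exclusions.** Criterion 11 (ALT, AST), criterion 12 (creatinine) and the potassium half of the electrolyte item each have an analyte in section 10.3.5. So 1 of the 2 electrolyte conditions in criterion 4 has a protocol-required test.

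6. **Does it depend on how the conjunction is read?** If either deficit excludes, a patient with normal potassium and unrecognised low magnesium passes. If both were required, a patient with low potassium could not be classified without a magnesium value. The gap exists either way.

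7. **Related inconsistency.** Section 3.4, in listing patients in whom the drugs will be avoided, names uncorrected hypokalaemia but not hypomagnesaemia, although that list is open-ended.

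**The case against.** The best reply is that the protocol does not forbid a magnesium test. Investigators take a history of all current conditions (10.1.2), review prior medication and may use existing site results, so a documented case is still excluded. Other exclusions also rest on history without a test, such as G6PD deficiency, HIV status and heart failure with reduced ejection fraction, for which Table 9-1 has no echocardiogram. QT protection is also layered: a screening ECG with a QTc(F) limit, measured potassium, a ban on QT-prolonging drugs from Visit 1 to Visit 5, exclusions for bradycardia, heart failure and arrhythmia, and ECGs at Visits 2, 3 and 4.

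Most of this stands. A reader might infer that the criterion gives no protection, or that it can never be checked. The documents do not support that, because documented and routinely detected cases are caught and the other safeguards operate.

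It does not close the gap. G6PD and HIV are expressly limited to known cases and this item is not. None of the other safeguards identifies low magnesium: the screening ECG finds prolongation already present. The later ECGs (10.3.3) are a pre-dose recording on Day 4(8) and recordings after the last dose, so they do not do the work of a screening test.

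**Conclusion.** The point holds as a minor, inexpensive improvement. Criterion 4 and section 10.3.5 do not match: the item applies to all uncorrected cases, but only those already documented or found in routine care can be excluded.

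Three stronger readings should be avoided.

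- **A count of ineligible patients.** A reader might multiply the 342 randomised by an assumed prevalence. The documents give neither a prevalence nor the share of cases that sites would find themselves, so no number is put forward.
- **Damage to the efficacy result.** Under section 12.2, enrolment of an ineligible patient is a violation that removes the patient from the CE and BE populations, and an undetected one would stay in. But the primary analysis is in mITT, which section 12.1 defines by inclusion criteria 3 and 4 and which keeps patients with violations. CE is supportive only. The documents show no route by which unrecognised low magnesium would bias a randomised, blinded comparison of clinical success.
- **Exposure to two QT-active drugs.** Each patient receives one of them (Table 6-1).

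The conclusion assumes that no manual outside these documents orders the test, and that the published list in section 10.3.5 is complete.

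**What to change.** Reconcile section 7.2 with section 10.3.5 and Table 9-1 by adding magnesium to the Visit 1 biochemistry list, run on the Day 1 sample. Because one list now serves Visits 1 to 4, mark the entry as Visit 1 only. The sponsor should state which reference limit is used, since criterion 4 gives none and the assay alone would not define the exclusion; no limit is suggested here. Section 3.4 should be aligned with the result.

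Cost: one analyte for each of the 382 patients expected at screening (12.10), so about 382 low-cost assays, normally on blood already drawn. The result must be back within the 24 hours allowed for Day 1 screening (Table 9-1, footnote 2); the documents do not say whether every local laboratory can do this. Where a site relies on results obtained before consent, an occasional extra draw may be needed, which works slightly against the aim of Amendment No. 3 to spare patients unnecessary sampling.
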